## 7.5 Analysis of Safety

In general, For AE Analysis up to Week 12 will be performed by Initial Randomization Set in SAF. AE Analysis from "Week 12 to the Last Evaluation" will be performed by Treatment Sequence Set in SAF. AE 100 Patient-Years analysis will be performed by Groups for Patient-Years. Details for analysis groups will be described in 10.3 Appendix3.

For other safety analysis except for AE up to Week 12 will be performed by Initial Randomization Set in SAF. For other safety analysis except for AE up to Week 52 will be performed by Treatment Sequence Set in SAF. Details for analysis groups will be described in 10.3 and 10.4.

### 7.5.1 Adverse Events

If an AE occurs on the same date as the initial dose date, the subject will be asked to select one of the following (see the eCRF page for AE): onset before initial dose of study drug,

onset after initial dose of study drug. Any AEs occurring after initial dose of study drug through the follow-up period will be considered treatment emergent.

Adverse events will be coded using the Medical Dictionary for Regulatory Activities (MedDRA).

All adverse events reported during the study period will be presented in subject listings.

Only TEAEs in the study period will be analyzed, and 2 types of analyses will be performed: TEAE occurrence analysis and TEAE per 100 patient-years analysis, as described below. TEAE occurrence analysis will be displayed by whole treatment period and by the following period. Primarily, TEAE occurrence analysis for Week 0 to Week 12 will be conducted in the view of comparison with placebo.

TEAE occurrence analysis for overall treatment period will be conducted in focus for ASP015K dose groups.

1. Week 0 to Week 12
2. Week 12 to Week 28
3. Week 28 to Week 52 or Later

TEAE per 100 patient-years analysis will be displayed above category, and by Week 0 to Week 12, and overall period.

#### **7.5.1.1 Adverse events**

The coding dictionary for this study will be MedDRA/J 11.1. It will be used to summarize AEs by SOC and PT. Subjects reporting more than one AE for a given MedDRA PT will be counted only once for that term. Subjects reporting more than one AE within a SOC will be counted only once for the SOC total. Subjects reporting more than one AE will be counted only once in the overall AE total.

SOCs will be presented by descending frequency for ASP015K Total column, and PTs within SOC will be presented by decreasing frequency in the ASP015K Total.

Number and percentage of subjects with TEAE in the following AE categories will be summarized by SOC and PT for each treatment group, ASP015K Total and Total:

An overview table will include the following details:

- Number and percentage of subjects with TEAE
- Number and percentage of subjects with drug related TEAE
- Number and percentage of subjects with death
- Number and percentage of subjects with serious TEAE
- Number and percentage of subjects with drug related serious TEAE
- Number and percentage of subjects with Grade 3 or Higher in Severity TEAE
- Number and percentage of subjects with TEAE leading to study drug discontinuation

- Number and percentage of subjects with drug related TEAE leading to study drug discontinuation
- Number and percentage of subjects with serious TEAE leading to permanent discontinuation of study drug or reference drug
- Number and percentage of subjects with drug related serious TEAE leading to permanent discontinuation of study drug or reference drug

The number and percentage of subjects with TEAEs, as classified by SOC and PT will be summarized for each treatment group. Summaries will be provided for:

- TEAEs
- Drug related TEAEs, defined as any TEAE with possible, probable or missing relationship to study drug as assessed by the investigator.  
Subjects reporting more than one TEAE for a given PT will be counted only once for that term in the most related category reported.
- Serious TEAEs
- Drug related serious TEAEs
- TEAEs by severity based on National Cancer Institute Common Terminology Criteria for Adverse Events (NCI-CTCAE) Grade (Grade 1 = mild, Grade 2 = moderate, Grade 3 = severe or medically significant, Grade 4 = life threatening, Grade 5 = death related to AE)  
Subjects reporting more than one TEAE for a given PT will be counted only once for that term in the most severe category reported.  
If a subject has an AE which has a missing severity, then the subject will be counted in the severity category of "Missing" (i.e., missing severity will not be imputed).
- Drug related TEAEs by severity
- Grade 3 or higher TEAEs by severity
- TEAEs by relationship to study drug  
Subjects reporting more than one TEAE for a given PT will be counted only once for that term in the most related category reported.  
TEAE with missing relationship to study drug missing will be counted as drug related. Moreover, any TEAE with missing relationship to study drug or reference drug was counted as drug related (probable).
- TEAEs leading to death
- TEAEs leading to permanent discontinuation of study drug
- Drug related TEAEs leading to permanent discontinuation of study drug
- Serious TEAEs leading to permanent discontinuation of study drug
- Drug related serious TEAEs leading to permanent discontinuation of study drug
- TEAEs excluding serious adverse events that equal to or Exceed a threshold of 5% in Any Treatment Group
- Most common TEAEs (> 5% in any treatment group)
- Most common serious TEAEs (> 5% in any treatment group)
- The number and percentage of subjects with TEAEs by subgroups defined in section 7.8

- The number and percentage of subjects with TEAEs of special interest.

Following adverse events of special interest are defined in the Appendix 10.8:

- Serious Infections
- Malignancies
- Herpes Zoster Related Disease (Herpes Zoster and Varicella)
- Herpes Zoster
- Varicella
- Infections That Require Intravenous Anti-infectious Therapy

In addition, the subgroup analysis of Sex, Age Group, Concomitant Steroid at Baseline, and Prednisone Dose at Baseline will be conducted.

### 7.5.1.2 Adverse Events Per 100 Patient-Years

In order to adjust for differences in subjects' durations in the study and the potential differential dropout rates between the treatment groups, TEAEs per 100 patient-years (PYs) will be calculated for each treatment group as follows:

#### Definition 1:

TEAEs per 100 PYs =  $100 \times (\text{Number of subjects who had at least 1 incidence} / \text{Total PYs})$

Total PYs will be calculated by summing individual subjects' durations.

If subjects had at least 1 predefined AE, then the duration of these subjects are summed as from initial dose up to first incidence of predefined AEs.

If subjects had no predefined AE, then the duration of these subjects are summed as from initial dose through follow-up. Summed duration will be divided by 365.25 to represent per year.

#### Definition 2:

TEAEs per 100 PYs =  $100 \times (\text{Number of TEAEs for all subjects in the treatment group} / \text{Total PYs in the treatment group})$ .

For number of TEAEs for all subjects in the treatment group, multiple occurrences of the same TEAE in the same subject will be counted multiple times.

Total PYs will be calculated by summing subjects' durations in study through the follow-up period. Each subject's duration will be calculated as:  $(\text{last date of follow-up in the study} - \text{date of initial dose of study drug} + 1) / 365.25$ .

Patient-Year analysis will be calculated by Placebo, 100 mg, 150 mg, 100mg+150mg, ASP015K Total, Total.

The number of TEAEs and AEs per 100 PYs will be provided by Definition 2, for all TEAEs (if analyzable), by SOC and PT for each treatment group, ASP015K Total and Total.

Patient-Year analysis for following specified AE will also be conducted by Definition 1 with 95% confidence interval.

- Serious Infections
- Malignancies
- Herpes Zoster Related Disease (Herpes Zoster and Varicella)
- Herpes Zoster
- Varicella
- Infections That Require Intravenous Anti-infectious Therapy

Note: Definition will be provided in the Appendix 8.

Confidence Interval for TEAEs per 100 patient-years will be calculated for AE of special Interest based on following formula (assuming Poisson distribution).

- Upper limit of CI (TEAEs per 100 PYs) :  $100 * \exp\left(\log\left(\frac{A}{T}\right) + Z_{\alpha} * \sqrt{\frac{1}{A}}\right)$
- Lower limit of CI (TEAEs per 100 PYs) :  $100 * \exp\left(\log\left(\frac{A}{T}\right) - Z_{\alpha} * \sqrt{\frac{1}{A}}\right)$

A: Number of subjects who had at least 1 incidence

T: Total PYs by 100 PYs as one unit

$Z_{(\alpha)}$ : alpha % point of standard normal distribution

alpha = 0.025

In addition, the subgroup analysis of Sex, Age Group, Concomitant Steroid at Baseline, and Predonisone Dose at Baseline will be conducted.

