## 6.2 Safety Variables

- AEs
- Vital signs (body temperature, pulse rate and blood pressure in sitting position)
- Body weight
- Central ECG
- 12-lead ECG
- Central electrocardiogram
- Chest radiography
- Laboratory assessments

**Treatment emergent adverse events** (TEAEs) will be defined as any adverse event that started or worsened in severity after initial dose of study drug through Week52 or Withdrawal.

AE for the subjects who switched ASP015K 100 mg or ASP150 mg from Placebo at Week 12 or Week 28 will be handled as follows.

- AE onset before the first dose of week12 study drug will be considered to be occurred at Placebo.
- AE onset after the first dose of week12 study drug before the first dose of week28 study drug will be considered to be occurred at Placebo if the subject did not switch Placebo at Week 12. Else, if the subject switched ASP015K 100 mg or 150 mg at Week12, then the AE onset after the first dose of week12 study drug before the first dose of week28 study drug will be considered to be occurred at ASP015K 100 mg or 150 mg.
- AE onset after the first dose of week28 study drug will be considered to be occurred at ASP015K 100 mg or 150 mg, which is switched treatment from Placebo.

A drug-related TEAE is defined as any TEAE with possible, probable or missing relationship to study drug as assessed by the investigator. Moreover, any TEAE with missing relationship to study drug or reference drug was counted as drug related (probable).

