SEQ2	150mg	ASP015K 150 mg	ASP015K 150 mg	ASP015K 150 mg	
SEQ3	Placebo to 100mg at Week 12	Placebo	ASP015K 100 mg	ASP015K 100 mg	
SEQ4	Placebo to 150mg at Week 12	Placebo	ASP015K 150 mg	ASP015K 150 mg	
SEQ5	Placebo to 100mg at Week 28	Placebo	Placebo	ASP015K 100 mg	
SEQ6	Placebo to 150mg at Week 28	Placebo	Placebo	ASP015K 150 mg	

- 100 mg: subjects who initially treated ASP015K 100 mg
- 150 mg: subjects who initially treated ASP015K 150 mg

- Placebo to 100 mg at Week 12: subjects who initially treated Placebo group and switched 100 mg at Week 12 and at least one dose of ASP015K 100 mg drug after switched
  - Placebo to 150 mg at Week 12: subjects who initially treated Placebo group and switched ASP015K 150 mg at Week 12 and at least one dose of ASP015K 150 mg drug after switched
  - Placebo to 100 mg at Week 28: subjects who initially treated Placebo group and switched ASP015K 100 mg at Week 28 and at least one dose of ASP015K 100 mg drug after switched
  - Placebo to 150 mg at Week 28: subjects who initially treated Placebo group and switched ASP015K 150 mg at Week 28 and at least one dose of ASP015K 150 mg drug after switched
- 
- The analyses for mTSS (Appendix 1, Appendix 2), erosion score, and joint space narrowing score will be performed at Week 28/ET and Week 52/ET, and statistical testing will also be conducted at Week 28/ET, Week 52/ET, compared with Placebo. These analyses include primary analysis (mTSS change from baseline at Week 28/ET).
  - MedDRA 11.1 will be used as the coding dictionary for adverse event and medical history.
  - Statistical hypothesis testing will be performed only if specified. All statistical comparisons of treatment groups will be versus placebo (i.e., each ASP015K treatment versus placebo) and will be made using two sided tests at the 0.05 significance level, unless stated otherwise. Multiplicity adjustment will be done in the primary analysis and other analysis if specified.
  - Statistical analysis including hypothesis testing for efficacy variables to compare 100 mg or 150 mg versus Placebo, only the data for the pairwise comparison will be used.
  - All statistical results will be presented, as appropriate, by treatment group, by treatment group and scheduled visit; the schedule of assessments is provided in 7.11.4.

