### Patient-year analysis

	Week 0 to Week 12	Overall Period
TEAEs	X1	X4
TEAEs of special interest	X1	X4
Serious Infections	X1	X4
Malignancies	X1	X4
Herpes Zoster Related Disease (Herpes Zoster and Varicella)	X1	X4
Herpes Zoster	X1	X4
Varicella	X1	X4
Infections That Require Intravenous Anti-infectious Therapy*	X1	X4
Subgroup		
Sex		X4
Age Group		X4
Concomitant Steroid at Baseline (No, Yes)		X4
Prednisone Dose at Baseline (mg/day) (None, 0 <- 5 mg/day, > 5 mg/day)		X4

X1: Placebo, 100mg 150mg

X4: 100mg 150mg

\*: subgroup analysis will not be conducted.

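### Overall adverse event rates per 100 patient-years split a switched subject's events at the switch but not the person-time, and the SAP does not settle which columns are affected

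*SAP*

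**What the plan says.** **Events.** SAP 6.2 divides a switched subject's events by date: "AE onset before the first dose of week12 study drug will be considered to be occurred at Placebo". Between Weeks 12 and 28, events follow the drug actually taken. After that, "AE onset after the first dose of week28 study drug will be considered to be occurred at ASP015K 100 mg or 150 mg".

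**Person-time.** SAP 7.5.1.2 gives two definitions. In Definition 1, a subject with an event contributes time up to the first one; for a subject without, "the duration of these subjects are summed as from initial dose through follow-up". In Definition 2, "Total PYs will be calculated by summing subjects' durations in study through the follow-up period", each duration being counted from the first dose of study drug. Neither mentions the switch.

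**Columns.** Under Definition 2 the SAP says: "Patient-Year analysis will be calculated by Placebo, 100 mg, 150 mg, 100mg+150mg, ASP015K Total, Total". SAP 7.5 says that "AE 100 Patient-Years analysis will be performed by Groups for Patient-Years" and sends the reader to Appendix 3 for details of the groups. The patient-year table there gives Placebo, 100 mg and 150 mg for Week 0 to Week 12. For the overall period it gives only "X4: 100mg 150mg". In the Treatment Sequence Set of SAP 7.1 the dose label is defined by starting treatment: "100 mg: subjects who initially treated ASP015K 100 mg".

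**Switching.** Under SAP 3.2, placebo inadequate responders switch at Week 12 and everyone still on placebo switches at Week 28. Every placebo subject who stays in the study is therefore affected.

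**The concern.** A rate per patient-year is meaningful only if an event counted in a column could have occurred in that column's time, and the reverse. Here events are divided at the switch and the written time is not. A placebo subject who stays to the end has 84 or 196 placebo days and spends the rest of the study on ASP015K, yet the formula gives one undivided duration.

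SAP 7.5.1.2 introduces these rates to adjust for differing durations, so the mismatch defeats their purpose. Definition 1 rates, with confidence intervals, are the planned summary for serious infections, malignancies and herpes zoster. If overall Placebo and ASP015K Total columns were printed, both could be materially wrong, and readers would compare them.

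**Working it through.** The SAP gives no person-time total or expected rate, so there is no plan figure to reproduce. The check compares person-time cut at the switch with person-time as written.

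**Inputs from the documents**
- 170 subjects per arm (SAP 4).
- Week 12 is Day 85 and Week 28 is Day 197 (SAP 7.11.1), so 84 or 196 days on placebo.
- Week 52 is Day 365, and follow-up is 4 weeks (SAP List of Key Terms), so 365 + 28 = 393 days. Subjects who enter the extension immediately have no follow-up visit; 365 days is the low case.

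**Assumptions**
- The share *s* of placebo subjects switching at Week 12 is not in the documents; 30%, 50% and 70% are used, with limits of 0 and 100%.
- No drop-out.
- ASP015K Total includes the switched subjects.

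**Formulas (Definition 2)**
- Mean placebo days per placebo subject: *p* = 84*s* + 196(1 − *s*).
- Events are the same either way, so printed rate ÷ correct rate = correct person-time ÷ person-time used. No assumption about the event rate is needed.
- Placebo, whole duration used: *p* ÷ 393.
- ASP015K Total, correct time per three subjects (one from each arm): 3 × 393 − *p* = 1179 − *p*.
- (a) Whole duration counted in both columns: ASP015K Total ratio = (1179 − *p*) ÷ 1179.
- (b) Whole duration kept in Placebo only: ASP015K Total ratio = (1179 − *p*) ÷ 786.

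| *s* | *p* (days) | Placebo, (a) and (b) | ASP015K Total, (a) | ASP015K Total, (b) |
|---|---|---|---|---|
| 0% | 196.0 | 0.499 | 0.834 | 1.251 |
| 30% | 162.4 | 0.413 | 0.862 | 1.293 |
| 50% | 140.0 | 0.356 | 0.881 | 1.322 |
| 70% | 117.6 | 0.299 | 0.900 | 1.350 |
| 100% | 84.0 | 0.214 | 0.929 | 1.393 |

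In patient-years at *s* = 50%: Placebo should have 170 × 140 ÷ 365.25 = 65.2 and would have 170 × 393 ÷ 365.25 = 182.9. ASP015K Total should have 170 × 1039 ÷ 365.25 = 483.6 and would have 548.7 under (a) or 365.8 under (b).

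(c) Whole duration moved to ASP015K only: ASP015K Total is low as in (a). Placebo keeps its pre-switch events but loses the switched subjects' time, so it is too high. With no drop-out its denominator is zero. As an illustration, let 10% (17 subjects) leave on placebo after a mean of 84 days, and 153 switch with *p* = 140. The rate is then (17 × 84 + 153 × 140) ÷ (17 × 84) = 22,848 ÷ 1,428 = 16 times too high.

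(d) Only subjects initially on 100 mg or 150 mg, with only their own events: no switch occurs, and the ratio is 1.

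With 365 days and *s* = 30, 50 and 70%, Placebo is 0.445, 0.384 and 0.322. ASP015K Total is 0.852, 0.872 and 0.893 under (a), and 1.278, 1.308 and 1.339 under (b).

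**The case against.** The strongest answer is that the mismatch never reaches a table. SAP 7.5 names Appendix 3 as the place where the patient-year groups are set out. Its overall period has only 100 mg and 150 mg, which by the SAP 7.1 labels exclude switched subjects, and the placebo comparison is confined to Week 0 to Week 12, before any switch. On that reading, case (d) applies and there is no bias from this source. This is a fair reading, and it stands as one of the possible outcomes.

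It does not close the point. It contradicts the six columns promised in 7.5.1.2. It also leaves open whether post-switch events, which 6.2 charges to 100 mg or 150 mg, are added to those dose columns; if they are, the mismatch returns there.

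A reader might infer that both the Placebo and ASP015K Total rates are certain to be too low. The documents do not support that. It requires a switched subject's whole duration to be counted in both columns, which the SAP nowhere says; under (b) ASP015K Total is too high and under (c) Placebo is. Nor does the SAP state that ASP015K Total differs from 100mg+150mg by the switched subjects. The separate listing makes this likely, but SAP 7.1 says only that all ASP015K groups are combined.

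Three limits on the size also stand. The switching share is assumed, drop-out is ignored, and the ratios are exact for Definition 2 only, because Definition 1 stops time at the first event. No hypothesis test depends on these rates.

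**Conclusion.** The point holds in conditional form. Events are cut at the switch and person-time as written is not, so numerator and denominator do not match in any overall-period column that includes switched subjects: Placebo, ASP015K Total, or the dose columns if post-switch events are added to them. The SAP also disagrees with itself on which overall rates will be produced.

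The direction and size depend on a rule that the SAP omits. With 30 to 70% switching at Week 12, no drop-out and 393 days:
- whole duration in both columns: Placebo 59 to 70% low, ASP015K Total 10 to 14% low;
- whole duration in Placebo only: Placebo equally low, ASP015K Total 29 to 35% high;
- whole duration in ASP015K only: ASP015K Total 10 to 14% low, Placebo high;
- Appendix 3 columns with initially randomised subjects only: no bias from this source.

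This should be corrected because it concerns the exposure-adjusted safety rates. It does not touch the primary efficacy tests.

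**What to change.** 1. Define the groups for the patient-year analysis once, and make the column list in 7.5.1.2 and the Appendix 3 table agree. Either dropping the extra columns from 7.5.1.2 or adding them to Appendix 3 would do; say in words how ASP015K Total differs from 100mg+150mg.
2. Under both definitions, for subjects initially on placebo, end Placebo person-time on the day before the first ASP015K dose and start ASP015K person-time at that dose. A subject who never switches keeps all their time in Placebo. Count each event in the interval in which it starts, as 6.2 already does.
3. If ASP015K Total is kept, add it to the Appendix 3 overall table on this basis. State whether switched subjects enter the 100 mg and 150 mg columns.

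The cost is SAP wording and one derived date per switched subject, with no new data. The printed rates may move in either direction, depending on which rule would otherwise have been programmed.

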#### **7.4.1.5 Time to the first response analysis**

Time to the first ACR20-CRP response analysis will be analyzed as following procedure. This analysis will be applied during first 12 weeks of treatment period, because placebo treated subjects can be switched to ASP015K after Week 12.

- Time to the first response analysis will be analyzed using KM profile plots for each treatment group, and log-rank test will be used for comparing each ASP015K dose group time-to-event profile versus placebo. This analysis will be applied up to Week 12.
- For each subject, time to the first event (days) will be defined as the number of days from the date of initial dose of study drug to the date the first occurrence of the event, and calculated as: date of the first occurrence of the event (most recent assessment among each components if the assessment date is different among each components) – date of initial dose of study drug +1. In addition to this, Cox proportional hazards model with a main effect for treatment group will be used comparing each ASP015K dose group versus placebo.
- Subjects who complete the treatment period through Week 12 without having the event will be censored at one day before the dosing at Week 12 day up to Day 92, and the censored time will be calculated as: one day before the dosing at Week 12 up to Day 92 – date of initial dose of study drug +1.
- In the time to response analysis, each subject will be classified as either a responder (event = 1 in time-to-event model) or a non-responder (event = 0 in time-to-event model), based on the definition in Section 6.1.1. The definition of event is the same as the definition of the binary response.
- Subjects who prematurely discontinued the treatment period through Week 12 (i.e. before the dosing at Week 12) without having the event up to Day 92 will be censored at the date of early discontinuation, and the censored time will be calculated as: date of early discontinuation from the treatment period up to Day 92 – date of initial dose of study drug +1.

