**Table10. Visit Window for Vital signs, laboratory test (hematology, biochemistry, urinalysis)**

Time points defined in analysis	Reference date*	Acceptable time range
Screening	Day -28 to Day -1	Day -28 to Day -1
Baseline	Day 1	Day 1
Week 4 to Week 48**	Day $7 \times x + 1$	Day $(7 \times x - 6)$ to Day $(7 \times x + 8)$ and before drug administration on the visit day
Week 52	Day 365	Day 358 to Day 372
Minimum on Treatment up to Week 12***		Minimum value at allowance Range (Day 2 to Day 92) before first dose of Week 12 study drug
Maximum on Treatment up to Week 12***		Maximum value at allowance Range (Day 2 to Day 92) before first dose of Week 12 study drug
Minimum on Treatment***		Minimum value during Entire Period (No limitation for period)
Maximum on Treatment***		Maximum value during Entire Period (No limitation for period)
Week 12/ET (Week 12 or at early termination before Week 12)	Day 85	Day 2 to Day 92
Week 28/ET (Week 28 or at early termination before Week 28)	Day 197	Day 2 to Day 204
EOT (Week 52 or at early termination)	Day 365	Day 2 to Day 372

\*: Day 1 represents the first day of study treatment. The day before is expressed as Day -1.

\*\* : Represents the reference date and acceptable time range for Week x.

\*\*\*: Applied to laboratory test only.

(2) Laboratory test (fasting lipid profile test)

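### The 95% limits for special-interest event rates apply the factor 100 twice and fail at zero events, and the Week 0–12 patient-year table has no person-time rule

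*SAP*

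**What the plan says.** SAP 7.5.1.2 gives two rates. Definition 1 is 100 times the number of subjects with at least one event, divided by total patient-years, with days divided by 365.25. Time stops at the first event; otherwise "If subjects had no predefined AE, then the duration of these subjects are summed as from initial dose through follow-up". Definition 2 counts all events over "durations in study through the follow-up period".

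For the events of special interest, Definition 1 rates get 95% limits of the form 100·exp(log(A/T) ± Z·√(1/A)), labelled per 100 patient-years. A is the number of subjects with an event, and T is given as "T: Total PYs by 100 PYs as one unit".

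On periods, SAP 7.5.1 states: "TEAE per 100 patient-years analysis will be displayed above category, and by Week 0 to Week 12, and overall period". The patient-year table in Appendix 3 (10.3) has a Week 0–12 column for group "X1: Placebo, 100mg 150mg" and an overall column for 100 mg and 150 mg. On groups, 7.5.1.2 states: "Patient-Year analysis will be calculated by Placebo, 100 mg, 150 mg, 100mg+150mg, ASP015K Total, Total".

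Elsewhere the SAP does cut at the Week 12 dose. In 7.4.1.5, subjects who complete Week 12 without a response "will be censored at one day before the dosing at Week 12 day up to Day 92". In Table 10 (7.11.5), the laboratory minimum up to Week 12 is the "Minimum value at allowance Range (Day 2 to Day 92) before first dose of Week 12 study drug". Section 6.2 assigns switchers' events to placebo or active drug according to the switch.

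**The concern.** Three gaps affect the same tables.

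- **Scale.** If T is already in units of 100 patient-years, A/T is already a rate per 100 patient-years, and the leading 100 scales it again. The limits then disagree with Definition 1.
- **Zero events.** The formula contains log(A) and 1/A. Malignancy, herpes zoster and varicella are separate rows, and some will probably be empty in Weeks 0–12.
- **Person-time.** A Week 0–12 rate needs a denominator that stops at Week 12. Neither definition stops there. For placebo, time through follow-up also includes time on active drug after the switch at Week 12 or Week 28.

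A related gap is that *ASP015K Total* is listed separately from *100mg+150mg*. SAP 7.1 explains combined columns in general. Nothing says whether this one includes switchers' time on active drug, and nothing splits their person-time as 6.2 splits their events.

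A secondary point is that Appendix 8 defines malignancies as a closed list of 12 preferred terms. It omits uterine sarcoma and chronic myelogenous leukemia, both reported earlier in the programme (protocol 1.4).

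These tables carry the exposure-adjusted rates and intervals for risks that protocol 1.4 singles out.

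**Working it through.** The documents state no rate or limit for this analysis, so there is no figure to reproduce. Z is read as 1.96, the upper 2.5% point.

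**1. Scale of the limits.** Take A = 5 and 170 patient-years (PY), an assumption of roughly one year for an arm of 170.

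- Rate, Definition 1: 100 × 5 / 170 = 2.94.
- As written, T = 170/100 = 1.7 and A/T = 2.941. The spread factor is exp(1.96 × √(1/5)) = exp(0.8765) = 2.4025. The limits are 100 × 2.941 / 2.4025 = 122 and 100 × 2.941 × 2.4025 = 707.
- With T = 170, the limits are 1.22 and 7.07.
- Exact Poisson limits are 100·χ²(0.025; 2A)/(2·PY) and 100·χ²(0.975; 2A+2)/(2·PY).

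| A | PY | Rate | As written | T = total PY | Exact |
|---|---|---|---|---|---|
| 1 | 170 | 0.59 | 8.3 to 418 | 0.08 to 4.18 | 0.015 to 3.28 |
| 5 | 170 | 2.94 | 122 to 707 | 1.22 to 7.07 | 0.95 to 6.86 |
| 10 | 170 | 5.88 | 317 to 1093 | 3.17 to 10.93 | 2.82 to 10.82 |

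The lower limit as written, divided by the point estimate, is 100·exp(−1.96/√A): 14 at A = 1 and 42 at A = 5, rising with A. The interval therefore excludes its own estimate for every A ≥ 1.

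**2. Zero events.** For 170 completers, person-time is 170 × 84 / 365.25 = 39.1 PY over 12 weeks and 170 × 364 / 365.25 = 169.4 PY over 52 weeks. The chance of no event is exp(−rate × PY / 100). The rate of 0.55 per 100 PY is the one protocol 1.4 cites for malignancies (excluding non-melanoma skin cancer) with another JAK inhibitor. The other rates are assumed.

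| Rate per 100 PY | Weeks 0–12 | 52 weeks |
|---|---|---|
| 0.55 | 0.81 | 0.39 |
| 1 | 0.68 | 0.18 |
| 2 | 0.46 | 0.03 |
| 3 | 0.31 | 0.006 |

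At A = 0 the SAP formula returns nothing. The exact upper limit is 100 × 3.689 / PY, which is 9.4 per 100 PY for 39.1 PY and 2.2 for 169.4 PY.

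**3. Week 0–12 person-time.** Suppose Week 0–12 events were divided by the person-time the SAP defines, 364 days without the 4-week follow-up or 392 days with it.

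- Completers: 364/84 = 4.33 and 392/84 = 4.67 times too much person-time. Three events in an arm of 170 would give 100 × 3 / 182.5 = 1.64 instead of 100 × 3 / 39.1 = 7.67 per 100 PY.
- Assuming 10% (17 of 170) leave at Week 6 and are followed for 4 weeks, each contributes 42 + 28 = 70 days to both denominators. Then (153 × 364 + 17 × 70)/(153 × 84 + 17 × 70) = 4.05, and 4.36 with 392 days.
- Share of a placebo completer's 364 days on active drug: (364 − 196)/364 = 46% after a Week 28 switch and (364 − 84)/364 = 77% after a Week 12 switch. On 392 days the shares are 43% and 71%.

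**The case against.** The strongest reply is that the doubled factor is a notation slip which the same section exposes. Definition 1 fixes the scale, the limits are labelled per 100 patient-years, and an interval of 122 to 707 around 2.94 would be noticed on the first output row. That makes a published error unlikely, but it leaves a final SAP whose stated rule is wrong.

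On zero events, the row would still show a rate of 0 and the missing limit would be visible. A stated rule would be enough; exact limits are one good choice. The 0.55 rate is for malignancies with a different drug, so it illustrates the malignancy row only. The formula still has no value at zero for any row.

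On person-time, the period is named as Week 0–12, and 6.2 uses the first Week 12 dose as the switch point for events. A sensible programmer would probably cut there. The factors of 4 to 4.7 therefore describe the stated definitions, not the likeliest execution. The SAP remains silent on the denominator.

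On groups, Appendix 3 assigns the overall period to 100 mg and 150 mg, which SAP 7.1 defines by initial treatment. That narrows the question but does not say what the separate *ASP015K Total* column contains.

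On the malignancy list, an unlisted malignancy is always serious (protocol Appendix 3) and a discontinuation criterion (protocol 3.4). It would still appear in the serious-event tables and listings, and should appear in the discontinuation tables. It would be missing only from the malignancy rows.

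**Conclusion.** The concern holds. Read as written, the limits are too high by exactly 100 and contradict Definition 1; this needs no assumption beyond the SAP's own definition of T. The absence of any limit at zero events is equally certain, and how often it would arise depends on the assumed rates and full retention. The person-time gap is real. Its size, about 4 to 4.7 times, applies only if the stated definitions are carried into the Week 0–12 table. The content of *ASP015K Total* and the malignancy list are secondary. All of this concerns descriptive safety tables, so no primary hypothesis test is affected, but the section should be corrected because these are the intervals for the key safety risks.

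**What to change.** In SAP 7.5.1.2:

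- Define T as total patient-years.
- Replace the log-normal approximation with exact Poisson (chi-square) limits, which also give an upper limit at zero events. At minimum, state a zero-event rule.
- For the Week 0–12 table, end person-time before the first Week 12 dose, or earlier at the first event (Definition 1) or end of follow-up. This matches 7.4.1.5 and Table 10.
- State whether *ASP015K Total* includes switchers' time on active drug. If it does, split person-time at the switch as 6.2 splits events.
- Secondary: use a full malignancy term grouping in Appendix 8.

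The cost is SAP wording and programming. All dates and events needed are already collected.
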